8.1 Administrative and General Procedures

8.1.1 Informed Consent

The investigator or medically qualified designee (consistent with local requirements) must obtain documented consent from each potential participant or each participant's legally acceptable representative prior to participating in a clinical study or future biomedical research. If there are changes to the participant's status during the study (eg, health or age of

majority requirements), the investigator or medically qualified designee must ensure the appropriate consent is in place.

8.1.1.1 General Informed Consent

Consent must be documented by the participant's dated signature or by the participant's legally acceptable representative's dated signature on a consent form along with the dated signature of the person conducting the consent discussion.

A copy of the signed and dated consent form should be given to the participant before participation in the study.

The initial ICF, any subsequent revised written ICF, and any written information provided to the participant must receive the Institutional Review Board/Independent Ethics Committee's (IRB/IEC's) approval/favorable opinion in advance of use. The participant or his/her legally acceptable representative should be informed in a timely manner if new information becomes available that may be relevant to the participant's willingness to continue participation in the study. The communication of this information will be provided and documented via a revised consent form or addendum to the original consent form that captures the participant's dated signature or by the participant's legally acceptable representative's dated signature.

Specifics about a study and the study population will be added to the consent form template at the protocol level.

The informed consent will adhere to IRB/IEC requirements, applicable laws and regulations, and Sponsor requirements.

8.1.1.2 Consent and Collection of Specimens for Future Biomedical Research

The investigator or medically qualified designee will explain the future biomedical research consent to the participant, answer all of his/her questions, and obtain written informed consent before performing any procedure related to the future biomedical research substudy. A copy of the informed consent will be given to the participant.

8.1.2 Inclusion/Exclusion Criteria

All inclusion and exclusion criteria will be reviewed by the investigator who is a qualified physician to ensure that the participant qualifies for the study.

8.1.3 Participant Identification Card

All participants will be given a participant identification card identifying them as participants in a research study. The card will contain study site contact information (including direct telephone numbers) to be used in the event of an emergency. The investigator or qualified designee will provide the participant with a participant identification card immediately after the participant provides written informed consent. At the time of intervention

allocation/randomization, site personnel will add the intervention/randomization number to the participant identification card.

The participant identification card also contains contact information for the emergency unblinding call center so that a healthcare provider can obtain information about study intervention in emergency situations where the investigator is not available.

8.1.4 Medical History

A medical history will be obtained by the investigator or qualified designee (refer to electronic case report form [eCRF] entry guidelines).

8.1.5 Gynecological History

A gynecological history (including menstrual history) will be obtained by the investigator or qualified designee for all participants. Special attention should be given to the gynecologic-related inclusion and exclusion criteria (eg, surgical confirmation of endometriosis, history of pelvic pain, characteristics of participant's menstrual cycle, previous gynecologic surgery, etc.). See Section 5.

As part of the gynecological history and to ensure the participant is eligible for study participation, the investigator or qualified designee will confirm that the participant has cyclic (secondary dysmenorrhea) AND non-cyclic, moderate to severe endometriosis-related pelvic pain, using an NRS (0-10 anchored with 0 [no pain] and 10 [extremely severe pain]). The participant's rating of her pain during her last 2 menstrual cycles must be an overall score of ≥ 5 to be eligible for participation in the study.

Pregnancy history (including gravidity and parity), including number of previous pregnancies and number of live births should be collected for all subjects at Visit 1 and reported on the appropriate eCRF.

8.1.6 Prior and Concomitant Medications Review

8.1.6.1 Prior Medications

The investigator or qualified designee will review prior medication use and record prior medication taken by the participant before screening. See Section 6.5 – Concomitant Therapy and refer to eCRF entry guidelines.

8.1.6.2 Concomitant Medications

The investigator or qualified designee will record medication, if any, taken by the participant during the study.

8.1.7 Rescue Medication (Naproxen Sodium) Dispensing and Instructions for Use

Naproxen sodium rescue medication (275 mg tablets) will be dispensed to each participant at Visits 2 through 6, inclusive. The investigator or qualified designee will instruct the participant on the proper use of the rescue medication according to local guidance.

Participants should be reminded that they should not take additional pain medication for ERP and that the naproxen sodium tablets provided by the Sponsor should be used only for ERP and not for other ailments during the course of the study.

Overdoses must be reported to the Sponsor (See Sections 8.5 and 10.3.1).

8.1.8 Rescue Medication Accountability

The use of naproxen sodium rescue medication will be reviewed at each study visit and during the telephone follow-up. An eDiary report will identify if a participant has taken an overdose of naproxen sodium based on the local labelling, and the investigator should follow up with the participant and report the overdose as appropriate.

8.1.9 Home Pregnancy Test Dispensing

Starting at Visit 2, participants will be given a urine pregnancy test (UPT) to take home. Additional UPTs for home use will be dispensed to participants as needed.

8.1.10 Assignment of Screening Number

All consented participants will be given a unique screening number that will be used to identify the participant for all procedures that occur prior to randomization. Each participant will be assigned only 1 screening number. Screening numbers must not be re-used for different participants.

Any participant who is screened more than once will retain the original screening number assigned at the initial screening visit.

Specific details on the screening visit requirements (screening/rescreening) are provided in Section 8.10.1.

8.1.11 Placebo Dispensing (for Run-In Period)

All participants will be dispensed single-blind, placebo run-in medication.

8.1.12 Assignment of Treatment/Randomization Number

All eligible participants will be randomly allocated and will receive a treatment/randomization number. The treatment/randomization number identifies the participant for all procedures occurring after treatment allocation/randomization. Once a treatment/randomization number is assigned to a participant, it can never be re-assigned to another participant.

A single participant cannot be assigned more than 1 treatment/randomization number.

8.1.13 Study Intervention Administration

The distribution of study intervention will be witnessed by the investigator and/or qualified designee at the study visits. Participants will receive either MK-7264 45 mg or placebo matched to 45 mg MK-7264. Participants should be instructed to take 1 tablet from the bottle bid.

Participants will be provided with enough study intervention to last between study site visits.

Study intervention should begin on the day of treatment randomization and will be administered at the study site at Visit 4. This first dose of study treatment at Visit 4 should be administered after the pre-dose PK sample collection and before approximately 11:00 AM. As dosing is bid, the next dose should be taken orally in the evening, approximately 12 hours later. Subsequent dosing will be performed by the participant (ie, unsupervised at her home) bid, approximately 12 hours apart at approximately the same time each day. However, on the day of a study site visit, the morning dose should not be taken at home and instead will be given as a witnessed dose at the study site after the pre-dose PK sample collection, and before approximately 11:00 AM. Participants should be contacted (eg, by phone or text) and reminded not to take their study intervention before a study site visit that includes pre-dose PK collection.

Participants who vomit after dosing or miss a dose should be instructed to continue with the next scheduled dose.

8.1.13.1 Timing of Dose Administration

Study intervention (ie, MK-7264 or matching placebo) will be administered orally, bid, approximately 12 hours apart for approximately 8 weeks (ie, two menstrual cycles) during the double-blind study treatment period.

8.1.14 Discontinuation and Withdrawal

Participants who discontinue study intervention prior to completion of the treatment period should be encouraged to continue to be followed for all remaining study visits.

When a participant withdraws from participation in the study, all applicable activities scheduled for the Discontinuation visit should be performed (at the time of withdrawal). Any AEs that are present at the time of withdrawal should be followed in accordance with the safety requirements outlined in Section 8.4 .

8.1.14.1 Withdrawal From Future Biomedical Research

Participants may withdraw their consent for future biomedical research. Participants may withdraw consent at any time by contacting the principal investigator for the main study. If medical records for the main study are still available, the investigator will contact the

Sponsor using the designated mailbox ([contact]). Subsequently, the participant's consent for future biomedical research will be withdrawn. A letter will be sent from the Sponsor to the investigator confirming the withdrawal. It is the responsibility of the investigator to inform the participant of completion of withdrawal. Any analyses in progress at the time of request for withdrawal or already performed prior to the request being received by the Sponsor will continue to be used as part of the overall research study data and results. No new analyses would be generated after the request is received.

In the event that the medical records for the main study are no longer available (eg, if the investigator is no longer required by regulatory authorities to retain the main study records) or the specimens have been completely anonymized, there will no longer be a link between the participant's personal information and their specimens. In this situation, the request for specimen withdrawal cannot be processed.

8.1.15 Participant Blinding/Unblinding

STUDY INTERVENTION IDENTIFICATION INFORMATION IS TO BE UNMASKED ONLY IF NECESSARY FOR THE WELFARE OF THE PARTICIPANT. EVERY EFFORT SHOULD BE MADE NOT TO UNBLIND.

For emergency situations where the investigator or medically qualified designee (consistent with local requirements) needs to identify the drug used by a participant and/or the dosage administered, he/she will contact the emergency unblinding call center by telephone and make a request for emergency unblinding. As requested by the investigator or medically qualified designee, the emergency unblinding call center will provide the information to him/her promptly and report unblinding to the Sponsor. Prior to contacting the emergency unblinding call center to request unblinding of a participant's treatment assignment, the investigator or who is a qualified physician should make reasonable attempts to enter the intensity of the AEs observed, the relation to study intervention, the reason thereof, etc., in the medical chart. If it is not possible to record this assessment in the chart prior to the unblinding, the unblinding should not be delayed.

In the event that unblinding has occurred, the circumstances around the unblinding (eg, date, reason, and person performing the unblinding) must be documented promptly, and the Sponsor Clinical Director notified as soon as possible.

Once an emergency unblinding has taken place, the principal investigator, site personnel, and Sponsor personnel may be unblinded so that the appropriate follow-up medical care can be provided to the participant.

Participants whose treatment assignment has been unblinded by the investigator or medically qualified designee and/or nonstudy treating physician must be discontinued from study intervention, but should continue to be monitored in the study.

Additionally, the investigator or medically qualified designee must go into the IRT system and perform the unblind in the IRT system to update drug disposition. In the event that the emergency unblinding call center is not available for a given site in this study, the IRT

system should be used for emergency unblinding in the event that this is required for participant safety.

At the end of the study, random code/disclosure envelopes or lists and unblinding logs are to be returned to the Sponsor or designee.

8.1.16 Calibration of Equipment

The investigator or qualified designee has the responsibility to ensure that any device or instrument used for a clinical evaluation/test during a clinical study that provides information about inclusion/exclusion criteria and/or safety or efficacy parameters shall be suitably calibrated and/or maintained to ensure that the data obtained is reliable and/or reproducible. Documentation of equipment calibration must be retained as source documentation at the study site.

8.2 Efficacy Assessments

8.2.1 Electronic Patient-reported Outcomes

8.2.1.1 eDiary Dispensing and Instructions

At Visit 2, each participant will be given a handheld electronic device containing the eDiary and will be properly trained and instructed on its use by the investigator or qualified designee. Participants should bring their eDiary device for all study visits, and should be contacted and reminded to do so (eg, by phone or text) before each visit.

Participants will be instructed to enter the *daily* eDiary information described below (Sections 8.2.1.2 through 8.2.1.6) on the evening of Visit 2, and every evening through study end. Preferably, this will be done at the same time each day (eg, before bedtime). Participants will be instructed to think only about the past 24 hours when completing the daily questions. If a participant forgets to enter the daily information, she will have 24 hours to do so.

Participants will also be asked to complete the daily eDiary entries from the previous day during Visit 2 (ie, while at the study site), if Visit 2 occurs more than one day after the last day of the previous menstrual bleeding.

If a participant discontinues early from study intervention, but agrees to be followed for the remaining study visits, she will be asked to continue completing the daily eDiary entries.

Completion of the daily questions in the eDiary is expected to take less than 10 minutes.

Participants will be instructed to complete the EHP-5 and PGIC (Sections 8.2.1.7 and 8.2.1.8) at the same time they complete their daily eDiary entries on the evenings of the visits indicated on the SoA. If these are forgotten, the participant will have 48 hours to complete them starting from the time when the visit is logged in to the eDiary.

Additional information for the site staff can be found on a secure online portal. Additional information for the participants can be found within the eDiary.

8.2.1.2 Pelvic Pain Severity Numeric Rating Scale

At the end of every day (just before she goes to bed), the participant will enter in her eDiary a rating of her worst pain or cramps in her pelvic area in the past 24 hours. This will be measured using a 0-10 NRS anchored with 0 (no pain or cramps) and 10 (extreme pain or cramps).

In order to confirm participant eligibility at Visit 3 and 4, study site staff will confirm that the participant has reported at least moderate pelvic pain during the SC and the BC as defined by average daily pelvic pain (cyclic and non-cyclic) score ≥ 5 .

8.2.1.3 Vaginal Bleeding or Non-bleeding Days

At the end of every day (just before she goes to bed), the participant will enter in the eDiary whether or not she had any vaginal bleeding during the past 24 hours and the amount of bleeding (eg, spotting, light, moderate, or heavy).

In order to confirm participant eligibility at Visit 3 and 4, study site staff will confirm that the participant's menstrual cycles before Visit 3 (SC) and Visit 4 (BC) were 24 to 38 days (inclusive) as documented in the eDiary.

8.2.1.4 Use of Rescue Medication (Naproxen sodium)

At the end of every day (just before she goes to bed), the participant will enter in the eDiary whether or not she took any of the pain relief tablets (naproxen sodium) provided by the study site in the last 24 hours. If yes, she will provide the number of tablets taken and the reason for taking them.

8.2.1.5 Use of Pain Relief Medication Other than Rescue Medication

At the end of every day (just before she goes to bed), the participant will enter in the eDiary whether or not she took any other pain relief medication (ie, other than the naproxen sodium provided by the study site) in the last 24 hours. If yes, she will provide the medication name (selected from a dropdown menu), dose, when taken, and the reason taken (ie, for ERP, other reasons, or ERP and other reasons).

In order to confirm participant eligibility at Visit 3 and 4, study site staff will confirm that the participant has taken only the study provided rescue medication for control of ERP during the SC and BC as evidenced in the eDiary. (Short term use (ie, ≤ 3 days) of other non-opioid pain medications for acute conditions other than ERP is permitted.)

8.2.1.6 Impact of Pelvic Pain

At the end of every day (just before she goes to bed), the participant will answer questions in the eDiary to assess the impact, if any, of pain or cramps in her pelvic area on the following items: limitations in paid work/work around the home/school work, limitations in physical activities, limitations in leisure or social activities and limitations on sleep.

8.2.1.7 Endometriosis Health Profile-5

The EHP-5 is an endometriosis-specific questionnaire to assess the participant's health-related quality of life at the beginning of the run-in period and at the end of TRC2.

Participants will complete the EHP-5 in the eDiary at approximately the same time in the evening as other eDiary entries on the day of the visits outlined in the SoA. The recall period on the EHP-5 is 'the last 4 weeks'. It is anticipated to take less than 5 minutes to complete.

8.2.1.8 Patient Global Impression of Change

The PGIC is a 7-point scale collecting a participant's rating of overall change in her ERP relative to her condition before initiation of the treatment.

At the end of TRC2, participants will complete the PGIC in the eDiary. The PGIC should be completed at approximately the same time in the evening as other eDiary entries on the day of the visit outlined in the SoA. It is anticipated to take less than 5 minutes to complete.

8.2.2 eDiary Compliance

Daily eDiary entries will be uploaded automatically into a secure online portal managed by the eDiary vendor. Sites will have access to reports within an automated database compiled from uploaded eDiary data which will be used to identify non-compliant subjects. Sites will not be able to view subject eDiary responses directly to prevent unblinding of site personnel.

Sites will monitor participant compliance in completing the following daily eDiary entries:

- Pelvic pain score,
- Vaginal bleeding,
- Rescue medication intake,
- Intake of pain relief medication other than the naproxen sodium provided by the Sponsor, and
- Impact of pelvic pain.

Participants must respond to each one of the daily eDiary questions in order to be considered compliant for a given day. Sites will review the compliance reports regularly and before every in clinic or telephone visit after Visit 2 to identify participants who have been non-compliant with the protocol. Participants who have been non-compliant with eDiary entry for 1 day should be contacted immediately. In order to confirm participant eligibility at Visit 3 and 4, study site staff will confirm that the participant has demonstrated compliance with $\geq 75\%$ of daily eDiary entries (Section 5.1).

Additionally, participants should be contacted any time that the reports indicate that the participant has used pain relief medication other than the rescue medication.

Sites are not required to continue to monitor eDiary compliance after a participant has discontinued study intervention.

The site is expected to make every reasonable effort to contact the participant (repeated calls, emails, text messages, etc.) to provide appropriate counseling. Site personnel must document any contact or attempted contact on a Subject Contact Log to be maintained at the site. Supplemental study visits may be scheduled for subject re-training.

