MK-7264/Placebo dispensing (For Double-Blind Treatment)				X	X					
MK-7264/placebo accountability				X	X	X			X*	V4: Participant must be ≥80% compliant with placebo run-in to be randomized. After randomization, see Section 6.4 for guidance if study intervention compliance is <80%.
Efficacy Assessments										
eDiary Dispensing; eDiary Instructions		X								
Pelvic Pain Severity NRS										If Visit 2 is > 1 day after last day of the previous menses, will be completed by participant using eDiary at site during Visit 2 (based on previous day). Also completed on evening of Visit 2 (based on Visit 2 day), and every subsequent evening.
Vaginal bleeding/Non-bleeding Day										
Use of rescue medication (naproxen sodium)										
Use of pain relief medication other than rescue medication provided by the Sponsor										
Impact of Pelvic Pain										
eDiary compliance			X	X	X	X	X	X	X	Participant compliance with daily eDiary entries must be ≥75% to be randomized. See Section 5.1. No compliance checks needed at visits after DC.
EHP-5			X			X			X*	

Study Period	Screening		Placebo Run-in	Treatment Period			Post Treatment Period			Notes
	Visit 1	Visit 2		Visit 3	Visit 4	Visit 5	Visit 6	Telephone Contact	Visit 7	
Visit Number	Visit 1	Visit 2	Visit 3	Visit 4	Visit 5	Visit 6	Telephone Contact	Visit 7	DC	End of menses = end of any visible menstrual flow Asterisk (*) in DC column indicates procedures not required if DC after V6. See Section 8.10.5 for procedures performed after DC.
PGIC						X			X*	
Collect eDiary								X	X	If participant discontinues study intervention and agrees to be followed, collection of eDiary will occur at last study visit.
Safety Assessments										
Complete Physical Examination	X									
Focused Physical Examination						X			X*	Focused physical exam: cardiovascular system, respiratory system, abdomen/gastrointestinal system, and extremities only.
Height	X									
Weight	X			X		X		X	X	
Calculate Body Mass Index (BMI)	X									
Gynecological Examination	X									Exam includes speculum insertion and bimanual examination.
Breast Examination	X									
Vital Signs (heart rate, blood pressure, temperature)	X		X	X	X	X		X	X	
12-Lead Electrocardiogram	X									
Hematology and Chemistry	X			X		X			X*	
Urinalysis (with microscopy)	X			X		X			X*	Participants with crystals/hematuria will be further evaluated (Section 8.3.8.1).

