8.10.5 Discontinued Participants Continuing to be Monitored in the Study

If a participant is discontinued from the study intervention early, the Discontinuation Visit assessments are to be performed as indicated in the SoA.

It is intended that all randomized participants should be followed through completion of the study, regardless of premature discontinuation of treatment, unless the participant withdraws consent from any study follow-up. Thus, participants who discontinue from study intervention before completion of the study should continue to be monitored after the Discontinuation Visit to obtain relevant information through the end of the study.

After the Discontinuation Visit, a telephone contact will be conducted 14 days following cessation of double-blind study intervention during which all reportable safety events as outlined in Section 8.4, [Table 3](#) will be collected. After the 14 day telephone contact, only drug-related SAEs will be collected; in addition, if the investigator becomes aware of any AEs (serious or non-serious) assessed as related to the rescue medication (naproxen sodium), they must be reported to the Sponsor.

Study site visits (or telephone contacts if scheduling of site visits is not possible) should occur at timepoints that correspond to each remaining study visit on the SoA. Only safety events as specified in the paragraph above and concomitant medication information will be collected at these visits. In addition, participants will be asked to continue to provide daily eDiary entries after discontinuation of study intervention; however, if a participant does not agree to continue using the eDiary, she will still be followed for collection of safety events as specified above and concomitant medication information.

Concomitant therapies specifically prohibited (see [Table 1](#)) while the participant was on study intervention are no longer prohibited after discontinuation of study intervention.

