9.5 Analysis Populations

9.5.1 Efficacy Analysis Populations

The Full Analysis Set (FAS) population will serve as the primary population for the analysis of efficacy data in this study. The FAS population consists of all randomized participants who have received at least one dose of double-blind study treatment and had at least one day of eDiary entry during the treatment cycle post randomization.

The modified Full Analysis Set (mFAS) population will be used as a supportive population for primary and secondary efficacy endpoints. The mFAS population consists of all randomized participants who have received at least one dose of double-blind study treatment, and had at least 10 days of eDiary entries in each of the treatment cycles post randomization.

The completer population will be used as a supportive population for primary and secondary efficacy endpoints, and will be used for the planned interim analysis. The completer population consists of all randomized participants who have completed the TRC2.

The Per-Protocol (PP) population will be used as another supportive population for primary and secondary efficacy endpoints. The PP population excludes participants from FAS due to important deviations from the protocol that may substantially affect the results of the

primary/secondary efficacy endpoint(s). Potential deviations that may result in the exclusion of a participant from the Per-Protocol population include:

- Compliance with <75% of eDiary daily entries
- No daily pelvic pain scores during TRC2

The final determination on protocol deviations will be made prior to the final unblinding of the database.

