9.6.1 Statistical Methods for Efficacy Analyses

This section describes the statistical methods that address the primary and secondary objectives. The primary analysis will be based on the FAS population, and supportive analyses will be based on the mFAS, Completer population and PP population.

The primary efficacy endpoint is the average daily pelvic pain score during TRC2. The variable of change from baseline in the average daily pelvic pain score will be used in the analysis of the primary endpoint. The primary analysis approach will be conducted utilizing the longitudinal analysis of covariance (ANCOVA) model. In this model, the response vector consists of the change from baseline in the average daily pelvic pain scores during TRC1 and TRC2. The model will include factors for average pelvic pain scores at baseline cycle, stratum, treatment, cycle, interaction of stratum-by-cycle, and the interaction of treatment-by-cycle as covariates. The model will use all available daily scores for calculating average pain scores during TRC1 and TRC2. The least-squares (LS) mean change from baseline at TRC2 with the associated standard errors (SEs) will be displayed for each treatment group; and the estimated treatment differences (MK-7264 – placebo) along with corresponding 95% CIs will also be presented.

The average daily pelvic pain score during TRC1 will be analyzed from the same model, and the LS mean (SEs, and 95% CIs) will be presented in the same way.

The secondary endpoints will be analyzed in the same way as the primary endpoint.

[Table 4](#) summarizes the key analyses strategies of the primary and secondary efficacy endpoints.

Table 4 Statistical Methods for Efficacy Endpoints

Endpoint/Variable (During TRC2)	Approach	Statistical Method	Analysis Population	Missing Data Approach
Primary				
Average daily pelvic pain scores during TRC2	P	Longitudinal ANCOVA	FAS	Observed data only
	S	Longitudinal ANCOVA	mFAS/Completer Population/PP	Observed data only
	S	Longitudinal ANCOVA	FAS	Jump to reference imputation
Secondary				
Average daily cyclic pelvic pain scores during TRC2	P	Longitudinal ANCOVA	FAS	Observed data only
	S	Longitudinal ANCOVA	mFAS/Completer Population/PP	Observed data only
	S	Longitudinal ANCOVA	FAS	Jump to reference imputation
Average daily non-cyclic pelvic pain scores during TRC2	P	Longitudinal ANCOVA	FAS	Observed data only
	S	Longitudinal ANCOVA	mFAS/Completer Population/PP	Observed data only

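### Sites need not check the diary once study drug is stopped, yet those women's Treatment Cycle 2 scores feed the primary analysis; keeping the check is a cheap guard against bias

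*Combined protocol and SAP*

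**What the plan says.** **While on drug.** Protocol Section 8.2.2 has sites review automated compliance reports regularly and before each visit or call, and adds: "Participants who have been non-compliant with eDiary entry for 1 day should be contacted immediately".

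**After drug is stopped.** The same section says: "Sites are not required to continue to monitor eDiary compliance after a participant has discontinued study intervention". The diary-compliance note in the Schedule of Activities (Section 1.3) agrees: "No compliance checks needed at visits after DC".

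**What is still wanted from these women.** Section 8.10.5 intends that "all randomized participants should be followed through completion of the study, regardless of premature discontinuation of treatment", and states that "participants will be asked to continue to provide daily eDiary entries after discontinuation of study intervention". A woman may decline the diary and still be followed for safety. The section schedules a visit or call at each remaining timepoint and asks for documented attempts to reach her, but limits what those contacts collect to safety events and concomitant medication.

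**What the analysis uses.** The Full Analysis Set (Section 9.5.1) needs one dose and a participant who "had at least one day of eDiary entry during the treatment cycle post randomization". For the primary longitudinal ANCOVA, Section 9.6.1 says: "The model will use all available daily scores for calculating average pain scores during TRC1 and TRC2". Table 4 gives the primary missing-data approach as observed data only. No cut at last dose and no minimum number of diary days is stated.

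**The concern.** The plan asks for diary scores after discontinuation and uses them in its primary analysis, but withdraws the required check at the point where a diary is most likely to lapse. If the entries do not arrive, the primary model relies on the missing-at-random assumption stated in sSAP Section 3.6.1.

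There is a plausible reason why such losses could differ by arm. Section 4.3.3 reports that 10% of participants at 50 mg bid in an earlier cough trial stopped treatment for taste effects, which are drug-related. If more women stop on MK-7264, more MK-7264 diaries go unchecked.

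At stake is the interpretation of the TRC2 difference. Daily scores that were never entered cannot be recovered at the analysis stage.

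**Working it through.** **1. Is the gap filled elsewhere?** Section 8.10.5 keeps visits, calls and contact attempts going, and Section 8.2.1.1 also asks for continued entries. None of these tells a site to look at the compliance report or raise missed entries. The sSAP compliance percentage (Section 3.5.1) runs to the day before Visit 7 or Discontinuation. If that means discontinuation of drug, later completeness is not measured either.

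**2. Would the planned sensitivity analysis catch a lapse?** Only in part.
- sSAP Section 3.6.1 defines the missing data to be imputed by jump-to-reference as a treatment cycle with no diary entry at all. A woman with a few TRC2 entries counts as observed.
- The same section starts TRC2 on the first non-bleeding day and ends it on the last bleeding day. A diary that tails off therefore loses the menstrual days: the combined average omits cyclic pain, and the cyclic secondary endpoint has no score.
- Bleeding is recorded in the same diary (Section 8.2.1.3), so the end of the cycle may be unknown too.
- The modified Full Analysis Set requires 10 diary days per treatment cycle, but it is supportive and excludes such women rather than keeping their data.

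**3. The plan's own power figure.** Inputs from Section 9.9: difference 1, SD 2, 70 per group, two-sided 0.05.

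Power = Φ(δ / (SD × √(2/n)) − 1.96) = Φ(1/0.338 − 1.96) = Φ(0.998) = 0.841, against the stated 84%. For 149, 146, 140 and 132 evaluable participants the formula gives 0.863, 0.856, 0.841 and 0.819, against 86%, 85%, 84% and 82% in Table 7. The plan's figures reproduce to within a percentage point.

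**4. Does keeping these women add power?** Table 7 holds the effect at 1 point for everyone evaluable. Women retained after stopping drug may keep all, some or none of it. Assume that the whole 15% loss is drug discontinuation (0.15 × 166 ≈ 25 women) and that SD stays 2.

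| Effect kept off drug | Half of the 25 retained (N ≈ 153; about 6 of 76.5 active women off drug) | All 166 retained |
|---|---|---|
| Full | effect 1, power 87% | effect 1, power 90% |
| Half | effect 0.96, power 84% | effect 0.925, power 85% |
| None | effect 0.92, power 81% | effect 0.85, power 78% |

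Average effects: 1 − 6/76.5 = 0.92 and 1 − 0.15 = 0.85 with none kept, and halfway from there to 1 with half kept. Power can rise or fall from 84%, because retention changes the effect being estimated as well as the precision.

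**5. Possible bias.** If a share m of an arm is missing and those women would have scored d points worse than the observed ones, the arm's observed mean looks m × d too good. The shift in the treatment difference is (m active − m placebo) × d. The documents give neither m nor d, so these values are assumptions.
- 20% v 10% missing, d = 1: 0.10 × 1 = 0.1 point in favour of MK-7264.
- 20% v 10% missing, d = 2: 0.10 × 2 = 0.2 point.
- 15% v 15% missing, equal d: 0.

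This is before any help from the TRC1 scores in the longitudinal model, which may reduce it.

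**The case against.** The strongest case for the plan is that follow-up is not abandoned. Section 8.10.5 schedules remaining contacts, asks for continued entries and has the consent form explain why continued data matter. Checking is made optional, not forbidden, and uploads are automatic. The sSAP expects little data to be missing not at random, and the model borrows from TRC1. The plan states no estimand, and therapies prohibited on drug are no longer prohibited afterwards (Section 8.10.5), so later scores may reflect other treatment. In a proof-of-concept trial, sparing sites some work is defensible.

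Much of this stands, and it limits the size of the point. A reader might infer that diary collection ends with study drug, or that the compliance check is the only thing sustaining it. Neither is so: what is lost is the required check and prompt. A reader might also take the missing data to be informative. That is a plausible risk, not a shown fact: the 10% comes from a cough trial at another dose, and stopping for taste need not relate to unobserved pain.

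The unstated estimand and the permitted later therapies do not defeat the change. The plan as written already requests and uses these scores. Scores that were collected can be set aside in a sensitivity analysis; lost ones cannot be restored.

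**Conclusion.** The point holds as a cheap improvement. The monitoring exemption works against the plan's own follow-up intent and primary analysis, and partial lapses in TRC2 would pass as observed data.

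Its size is modest and conditional: 0.1 to 0.2 point on a planned effect of 1 under the assumed 10-point imbalance and 1 to 2 point difference, and 0 if missingness and the pain difference are balanced.

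Two stronger readings are not supported. A reader might take Table 7 to show that retaining these women raises power, for example to 87%. That needs the full 1-point effect to persist off drug, which nothing in the documents establishes, so no power gain should be claimed. A reader might also conclude that about 25 women are affected. The 15% in Section 9.9 is expected drop-out, taken from cough trials. It may include women who withdraw consent, whom no diary check can retain, and the documents give no separate rate of drug discontinuation. Twenty-five is therefore an upper figure under the planned rate. Nor does the point move reliance to jump-to-reference, which remains supportive.

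**What to change.** - Delete the exempting sentence in Section 8.2.2 and the matching note in the Schedule of Activities.
- Require sites to keep reviewing the existing automated reports and to prompt women who agreed to continue the diary, at least to the time corresponding to Visit 6. Women may still decline the diary, as Section 8.10.5 allows.
- Align the Section 8.10.5 sentence that limits post-discontinuation contacts to safety events and concomitant medication, so that diary review is not excluded.

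Cost: a little site time and some extra contact with women who stop drug early, at most about 25 if all of the planned 15% loss were drug discontinuation. No new system or procedure is needed.
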